9.2.3 Randomisation

Eligible subjects will be centrally randomised using an IRT system after checking inclusion and exclusion criteria and before the first intake of the IMP. Randomisation may take place on Day -1, provided all the required examination results are available to assess subject eligibility in relation to the inclusion and exclusion criteria.

Randomisation in the trial is described in the Study Operations Manual.

9.2.4 Treatment Period

The procedures to be performed each day during the treatment period are presented in the Schedules of Events for Part 1 and Part 2 (see Appendix 1 and Appendix 2) and a flow-chart is provided in the Study Operations Manual, with a day-to-day description of the various visits.

It is important that each procedure for an individual subject is performed at around the same time each day throughout the treatment period.

Some procedures are to be performed before IMP administration and others after IMP administration (see below for details).

Note that not all procedures are to be performed at each study visit (see the Schedule of Events for information on which ones to perform).

9.2.4.1 Procedures routinely to be performed before IMP administration

- Collection of pre-dose AEs (see Section 9.3.4).
- Collection of pre-dose concomitant medications (see Section 8.1 and 9.3.1.3)
- Laboratory safety, including haematology, biochemistry and urinalysis (see Section 9.3.3.9.1)
- Pregnancy test in WOCBP (see Section 9.3.3.9.3)
- Collection of exploratory samples
- Pre-dose PK blood sampling (see Section 9.3.2)
- Vital signs (see Section 9.3.3.6)

The IMP must be administered to subjects with food (see Section 9.2.8), except for ivermectin or matching placebo at Month 6 in Part 2, which must be administered in the fasting state.

9.2.4.2 Procedures routinely to be performed after IMP administration

- Full or shortened symptom-directed physical examination (see Section 9.3.3.3)
- Brief neurological examination (see Section 9.3.3.4)
- Collection of post-dose AEs (see Section 9.3.4)
- Collection of post-dose concomitant medications (see Section 8.1 and 9.3.1.3)
- 12-lead safety ECG (see Section 9.3.3.8)
- Post-dose PK blood sampling (see Section 9.3.2)
- Ophthalmological examination (see Section 9.3.3.7)
- Skin snip (see Section 9.3.3.1.1)

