8.3 Ivermectin: Rescue Medication, Post-Study, Screening Failures

Ivermectin used as described in this section for rescue medication or post-study will be provided as a single oral administration at the approved dose of 150 μ g/kg bw and is not an IMP, i.e. will not be presented as over-encapsulated tablets.

When ivermectin is administered at a follow-up or early termination visit, it must be administered only after completion of the procedures scheduled at that visit, and after confirmation of last menstrual period and a negative pregnancy test. Ivermectin will be administered to subjects under fasting conditions.

Subjects who fail screening in the communities or at the investigational centre will be referred to the National Program PNLMTN-CTP for MDA with ivermectin.

8.3.1 Rescue Medication in Part 1

In Part 1, ivermectin will be administered as rescue medication at any time during the study, at the investigator's discretion, to subjects with clinically significant worsening of symptoms and/or signs related to onchocerciasis.

8.3.2 Rescue Medication in Part 2

In Part 2, ivermectin will be proposed as rescue medication to all subjects with clinically significant worsening of symptoms and/or signs related to onchocerciasis at any time during the study and/or to subjects with increased mean number of skin microfilariae at Month 18, compared to the mean number at Month 12.

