- 1. Some screening procedures will be conducted in subjects' communities.
- 2. For each subject, a given procedure should as far as possible be performed at the same time of day every time it is scheduled throughout the study to minimise variability. Also note that on IMP administration days, some procedures must be performed pre-IMP intake and others post-IMP intake. See Section 9.2.4 for details and other footnotes herein.
- 3. Screening procedures will be performed only after obtaining the main written informed consent
- 4. Skin snips will be used to assess O. volvulus skin microfilarial density at the indicated time-points.. Four skin snips per time-point (iliac crests and calves on both sides).
- 5. Blood sampling including evaluation in blood of Wuchereria bancrofti, Mansonella perstans and Loa loa.
- 6. Nodule palpation and documentation of onchocerca nodules.
- 7. Details of the physical examinations will be specified in the Study Operations Manual. To include height and weight at Screening, and within 2 days prior to first intake of IMP.
- 8. A short symptom-directed neurological examination will be conducted. Details of the examination will be specified in the Study Operations Manual.9. At the time-points indicated, a shortened symptom-directed physical examination will be conducted. Details of the examination will be specified in the Study Operations Manual.
- 10. Pregnancy testing may be urine or serum, except for test at screening at the site and at Day 13 visit, (or Early Termination Visit if done before Day 13) which must be serum. In case a repeat is needed during screening at the site, test can be urine providing the initial testing was serum and this was approved by the sponsor. Test at the Day 13 visit will be done at least 24 hours after the last IMP intake.
- 11. The Investigator will arrange for a highly effective form of birth control (as detailed in Section 8.2) if required. Must be discussed at Screening, checked within 2 days prior to first intake of IMP, checked at the time-points indicated and documented. In each case of delayed menstrual period (over one month between menstruations) confirmation of absence of pregnancy with a pregnancy test is mandatory. This recommendation also applies to WOCBP with infrequent or irregular menstrual cycles.
- 12. Supine blood pressure (SBP, DBP), supine heart rate, respiratory rate and oral temperature

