- 13. Ophthalmological examinations: full ophthalmological examination includes ocular symptoms, ocular examinations including ocular alignment, mobility and pupillary response, visual function (visual acuity, visual field, colour vision), retinal examination and fundus photography, slit lamp examination of anterior and posterior segments and intraocular pressure. Eye microfilarial count and data for clinical outcomes in the eye will be recorded during the ophthalmological examination.
- 14. Assessments for clinical outcomes (see Study Operations Manual for details) in the skin to be performed during physical examinations where the time-points coincide.
- 15. 12-lead ECGs will be recorded in triplicate with 1 minute between recordings at all time-points. ECGs will be performed 1-2 h after intake of the IMP. ECG at early termination is only applicable if early termination is before Month 3.
- 16. Blood and urine samples for clinical laboratory safety tests (haematology, biochemistry & urinalysis (plus urine microscopy where indicated if urinalysis is abnormal and clinically significant).
- 17. IMPs will be administered daily on site and IMPs dispensation will be done via the IRT system. Treatment duration and IMPs dispensation scheme will be confirmed before start of the Part 2, depending on the regimen selected.
- 18. Administration of ivermectin must be only after completion of the procedures scheduled at the visit (including nodulectomy where scheduled), and after a negative pregnancy test. Rescue medication (ivermectin) will be offered at the investigator discretion to administer if worsening symptoms and/or signs related to onchocerciasis at any time throughout the study and/or to patients with increased mean microfilaria in the skin at Month 18, compared to the Month 12 mean value.
- 19. AE collection from signature of Informed Consent onwards. AE monitoring will be performed as specified in Section 9.3.4 and will include scheduled questioning at the indicated time-points.
- 20. In the event of certain AEs considered to be associated with the IMP, additional examinations may be conducted in order to better interpret the AE, including safety laboratory, PK, ophthalmological, physical, neurological and parasitological (eye and skin) examinations.

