- 21. Blood samples for dry blood spot assay (PK) of ABBV-4083 and albendazole sulfoxide will be taken on Day 0: 0h (any time before dosing), 1h, 2h, 3h, 4h, 6h and 12h (+/- 15 minutes for all); and Day 1 at 0h (up to 30 min prior dosing. Samples on Day 6 and 13 will be collected between 2 and 4 hours after dosing. Schedule to be confirmed based on data from Part 1

Confidential Page 103 of 112

- 22. Blood and urine samples will be collected at the time-points indicated and stored for future analysis (for example: biomarkers, immunological markers testing). Note: in addition, where feasible, tissue samples collected from other procedures during the study (e.g. skin, nodules etc.) will also be stored after analysis. Subjects have the possibility to opt out of exploratory samples.
- 23. Nodulectomy must be performed only after completion of the other procedures at the visit.
- 24. In-house Period will have one additional day on D13 for observation post last dose and to perform pregnancy test at the end of exposure period.
- 25. Post-nodulectomy wound care will continue for up to approx. 2 weeks. The subject may go back to the community or may stay at the investigational site for logistic reasons or if medically indicated. End of Study visit will be 2 weeks after nodulectomy. The visit may be performed in the community
- * Repeat period can be extended to 7 days in exceptional circumstances, with prior agreement with the Sponsor (exception of pregnancy test which must be repeated within
- 2 days and can be urine if serum test was already done)

Confidential Page 104 of 112

Appendix 3. Total Blood Volume to be Collected in Part 1

The blood volume planned to be collected from each subject during the Part 1 of this study is detailed in Table 9, rounded up to the nearest 1 mL. Additional samples may be required in the event of AEs.

Table 9. Total Blood Volume in Part 1

Test	Planned number of tests	Volume (mL)	Total planned blood volume (mL)					
Pregnancy serum test	2	Screening and Day 13:0 (on biochemistry tube)	0					
Parasitology - microscopy Parasitology - RDT	1	4 1	5					
Haematology	5	4	20					
Biochemistry	5	5	25					
Pharmacokinetics	11	1	11					
Exploratory samples	3	5	15					
Cannula discard	7	1	7					
Total blood volume	Total blood volume to be collected in Part 1 per subject 84							

RDT: rapid diagnostic test

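### Section 9.2.4.2, read literally, puts the Month 6 skin snips and eye examination of Part 2 after the ivermectin dose, in conflict with other passages on order

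*Protocol*

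**What the plan says.** Protocol Section 9.2.4 splits procedures into a pre-IMP list (9.2.4.1) and a post-IMP list (9.2.4.2, headed "Procedures routinely to be performed after IMP administration"). The post-IMP list contains "Skin snip (see Section 9.3.3.1.1") and "Ophthalmological examination (see Section 9.3.3.7"). Neither is in the pre-IMP list.

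The section is not confined to the in-house days. Section 9.2.4.1 says that IMP is taken with food, "except for ivermectin or matching placebo at Month 6 in Part 2, which must be administered in the fasting state". In Appendix 2, Table 8, the Month 6 column carries footnote 2, which says that "on IMP administration days, some procedures must be performed pre-IMP intake and others post-IMP intake" and refers to Section 9.2.4 for details.

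Three other passages bear on order:

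- Section 8.3 has ivermectin given at a follow-up visit only once that visit's procedures are done. It opens by limiting itself to rescue and post-study ivermectin, which "is not an IMP, i.e. will not be presented as over-encapsulated tablets".
- Table 8 footnote 18 states: "Administration of ivermectin must be only after completion of the procedures scheduled at the visit (including nodulectomy where scheduled"). Its marker is on the rescue row (Months 18 and 24, early termination). The IMP row carries footnote 17, which is silent on order.
- Table 8 footnote 23 states: "Nodulectomy must be performed only after completion of the other procedures at the visit". It applies to the Month 6 nodulectomy of the Alternative Scenario.

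**The concern.** Section 2.4.2 describes ivermectin as killing microfilariae quickly. If Month 6 snips are taken after the dose, then in arms that receive ivermectin they no longer measure only the six-month effect of the initial regimen. In Arm L, which receives placebo at Month 6, they still do.

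Arms K and L have the same regimen up to that dose (Section 3.3), so their expected Month 6 difference before dosing is zero, and post-dose snips could create one. They could also flatter Arm N1, which has had no active initial regimen by then.

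The results at stake are the Part 2 secondary endpoints of skin-microfilaria-free status and density reduction at Month 6 (Section 5.2.2) and the exploratory eye counts at Month 6 (Section 5.3).

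**Working it through.** The plan gives no figure to reproduce here. The check compares the schedule rows with the order lists and then counts subjects.

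**Step 1. Which scheduled visits have both IMP and skin snips?**

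- Part 1 (Appendix 1, Table 7): IMP on Days 0 to 13; snips at Screening, Months 3 and 6, and early termination. No scheduled overlap. The Month 6 ivermectin of Part 1 is post-study and so not an IMP (Sections 8.3 and 8.4).
- Part 2 (Appendix 2, Table 8): IMP on the in-house treatment days and at Month 6; snips at Screening, Months 3, 6, 12, 18 and 24, and early termination. The scheduled overlap is Month 6 only.

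The skin-snip line therefore either governs Month 6 of Part 2 or has no scheduled use. The eye-examination line differs: it also applies on Day 13 of Part 1, an IMP day without ivermectin, so it has a legitimate use there.

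**Step 2. Who receives ivermectin at Month 6?** Arm sizes are from Section 3.3.

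- Base Scenario: K 84 + N1 42 = 126; 126/294 = 43%.
- Base Scenario with M on ivermectin: 126 + 84 = 210; 210/294 = 71%.
- Alternative Scenario: K alone, 84/336 = 25%; with M and N2 also on ivermectin, 84 + 84 + 84 = 252; 252/336 = 75%.

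These are counts of exposed subjects, not estimates of bias.

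**Step 3. Can the bias be sized?** Let p be the expected proportion free of skin microfilariae just before the Month 6 dose, equal in K and L. Let f be the share of still-positive subjects whose snips become negative between dose and snip. The spurious K minus L difference is

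[p + f(1 − p)] − p = f(1 − p),

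which runs from 0 when f = 0 to 1 − p when f = 1. The documents give neither p nor f, nor the interval between dose and snip. No value follows.

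**Step 4. Do the other passages settle the order?** Section 8.3 and footnote 18 either stay within rescue and post-study use, leaving 9.2.4.2 as the only list that places Month 6 snips relative to IMP, or they are general and contradict 9.2.4.2. Both readings need a correction. Section 7.3.2.2 adds that the Month 6 dose is taken fasting and that IMPs are given at about the same time each morning, which makes dosing first plausible in practice.

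**The case against.** The strongest reply is that 9.2.4.2 was never meant to order the Month 6 endpoint snips. Its skin-snip line cites Section 9.3.3.1.1, on screening parasitology, and not 9.3.3.1.2, which describes the efficacy snips. Section 9.2.4 is headed as the treatment period, whereas Table 8 classes Month 6 as out-patient, and follow-up visits fall under 9.2.5. The Month 6 remark in 9.2.4.1 concerns food. Footnote 2 also sits on visits with no IMP. The lists describe what is routine, and footnote 18 opens in general terms. The Study Operations Manual flow-chart, not among the documents, may settle the matter.

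Much of this stands. The cross-reference does suggest a drafting error, and the broad reading of 8.3 and footnote 18 is tenable. But screening snips cannot follow IMP, so the cross-reference does not give the line a valid use. The broad reading makes the protocol contradict itself, and a site flow-chart should not have to override the protocol.

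Three stronger inferences are tempting and are not supported:

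- A reader might take footnote 23 to place the Alternative Scenario nodulectomy after ivermectin. That requires IMP intake to count as a procedure, and footnote 2 treats procedures and IMP intake as separate things. The order is unclear, not stated.
- A reader might conclude that a needed pre-ivermectin reference is lost. The objective on the Month 6 dose is set at Months 12, 18 and 24 (Section 3.1), K and L are randomised, and density reduction is measured from baseline (Section 5.2.2). No analysis is specified that uses Month 6 as a reference.
- A reader might use the visit window of one month either way to argue that snips could follow the dose by days. The window governs when the visit occurs, not the interval within it.

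**Conclusion.** The concern holds as an internal conflict on the order of assessments at one visit. On its literal wording, 9.2.4.2 puts Month 6 skin and eye microfilaria results of Part 2 after ivermectin in 126 to 210 of 294 Base Scenario subjects, or 84 to 252 of 336 in the Alternative Scenario, but never in Arm L.

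This assumes that 9.2.4 applies to the Month 6 dose, as 9.2.4.1 and footnote 2 indicate, and that no site document overrides it. It does not show that sites will work in that order.

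The direction of any bias is clear: the ivermectin arms would look better at Month 6. Its size is not known and could be small if snips follow the dose closely. A reader might fear for the main results, but the Month 24 primary and key secondary endpoints and all of Part 1 are unaffected. The SAP covers Part 1 only and does not resolve the point. The correction should be made before Part 2 opens, because it is cheap and protects results that the plan intends to report.

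**What to change.** Delete the skin-snip entry from Section 9.2.4.2. State once, in 9.2.4.1 and as a footnote on the Month 6 IMP cell of Table 8, that at Month 6 of Part 2 the skin snips and eye microfilaria counts are collected before ivermectin or matching placebo. Keep the eye-examination entry in 9.2.4.2 for the in-house days, with Month 6 of Part 2 excepted.

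Reconcile Section 8.3 and Table 8 footnotes 18 and 23 with this. The protocol should also say where the Alternative Scenario Month 6 nodulectomy falls relative to the dose; that order is for the sponsor and investigators to decide.

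The cost is protocol wording and the site flow-chart. The Month 6 dose is given slightly later in the visit; the dose itself and the visit schedule do not change. The pause between Part 1 and Part 2 is a natural time to do it.

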9.2.5 Follow-up Period

All the procedures that need to be performed at every follow-up visits are listed in the Schedules of Events for Part 1 and Part 2 (see Appendix 1 and Appendix 2) and a flow-chart will be provided in the Study Operations Manual to indicate a description of the different visits.

9.2.6 Early Termination Visit

See also Section 6.5.

All of the procedures to be performed at the early termination visit (unless the subject withdraws consent for some or all, as described in Section 6.5) are listed in the Schedules of Events for Part 1 and Part 2 (see Appendix 1 and Appendix 2) and a flow-chart will be provided in the Study Operations Manual to describe the visit.

9.2.7 Accommodation

During the In-house Period, subjects in Part 1 and Part 2 will stay in or close to the investigational centre, which will be in or close to a hospital, for completion of screening, during the treatment, and for observation after the last intake.

Subjects will return to the centre for follow-up visits.

Subjects may remain in the investigational centre for nodulectomy. Overnight accommodation may be provided at other times, associated with study visits for logistical reasons or social reasons or in the event of technical issues.

9.2.8 Dietary and Lifestyle Guidelines in Parts 1 and 2

The dietary and lifestyle guidelines for subjects in Part 1 and Part 2 are presented in Table 6.

Table 6. Dietary and Lifestyle Guidelines - Part 1 and Part 2

Parameter	Guidelines	
Grapefruit and grapefruit juice	Subjects will be instructed not to consume grapefruit from 7 days prior to IMP administration until 24 hours after the final intake of the IMP.	
Alcoholic drinks	Subjects will be instructed: - not to consume alcohol from 48 hours prior to IMP administration until the end of the in-house period; - not to consume alcohol for 24 hours before each out-patient follow-up visit; - not to consume more than 3 units per day (1 unit = 250 mL of beer or 25 mL of spirits) at any time up to the 3-month visit; - to avoid excessive use of alcohol at all other times during the study.	
Caffeinated drinks	No restriction	
Smoking	Subjects will be instructed not to smoke from 24 hours prior to IMP administration until 24 hours after the last IMP administration.	
Food and water intake	On the days when laboratory safety samples are collected, the subjects will fast for at least 8 hours prior to sample collection. During the in-house period, standard local meals will be provided at usual times designated by the Investigator. The meal contents will be recorded in the source documents and the timing with respect to IMP administration and that it was consumed will be recorded in the source documents and in the eCRF. IMP should be administered with food. Subjects will be allowed to drink water ad libitum at all times during the study.	
Drugs of abuse Subjects will be instructed these are prohibited throughout the study.		
Driving and operating of machinery	No studies have been performed on ABBV-4083 or Albendazole regarding the effects on the ability to drive and use machines. Subjects will remain in or close to the research centre during the treatment period, however as a precaution they will be advised to avoid these activities between the first intake of IMP and up to 2 days after the last intake of the IMP.	

9.3 Summary of Study Procedures and Assessments

9.3.1 Subject Characteristics

9.3.1.1 Demographic Data

The following demographic data items will be recorded in the eCRF:

Year of birth and/or age;

- Sex:
- Ethnic origin;
- · Body weight;
- · Height.
- Town and/or district of residence.

9.3.1.2 Medical History

The following medical history items will be recorded:

- Relevant past medical history, including prior diseases with start and end dates, prior treatment with start and end dates (see Section 8.1);
- Surgical history, including indications and dates;
- Current medical history, including start date and grade of on-going conditions;
- Symptoms of onchocerciasis disease (ocular, skin, other).

9.3.1.3 Concomitant Medication

The following items for concomitant medication will be recorded:

- International non-proprietary name (i.e. generic name); dose, frequency, route of administration and indication;
- Start and stop dates

9.3.2 Pharmacokinetics and Pharmacodynamics

Blood samples for PK analyses of ABBV-4083 and albendazole sulfoxide, i.e. the active metabolite of albendazole, will be collected in Parts 1 and 2 at the time-points indicated in the Schedule of Events (see Appendix 1 and Appendix 2). A dry blood spot collection method will be used, for which detailed instructions will be included in the Laboratory Manual. The PK analyses will be performed using validated analytical methods. Since the PK calculations will be based on actual sampling, dosing times, and content of the meal provided with dosing, the data must be thoroughly documented in the subject's medical file and/or eCRF.

The PD effect of ABBV-4083 and of albendazole sulfoxide, the active metabolite of albendazole, on *Wolbachia* levels in female adult worms, status of female adult worm and skin microfilariae will be assessed in Parts 1 and 2 with regard to the PK parameters of ABBV-4083 and albendazole (see also Section 9.3.3.1).

